4.0 SUBJECT SELECTION

4.1 Inclusion Criteria

The following conditions must be met before a subject may be enrolled in the study.

- 1. Willing to give written informed consent, able to make the required study visits and follow study protocol instructions.
- 2. Willing to consent to gene mutation typing. Mutation typing will be restricted to typing for eye disease-related genes known to be involved in inherited retinal degenerations and related disorders. If typing results are already available for the subject, the previous results can be recorded and this requirement is waived.
- 3. Clinical diagnosis of RP confirmed by ERG.
- 4. BCVA 20/200 or worse and no worse than HM in cohort 1; and BCVA 20/40 or worse and no worse than 20/200 for the second cohort.
- 5. Male or female, age \geq 18 yr.
- 6. Adequate organ function:
 - a. blood counts (hematocrit, Hgb, WBC, platelets and differential) within normal range, or if outside of normal range, not clinically significant as judged by the investigator
 - b. liver function: alanine transaminase [ALT] and aspartate transaminase [AST] ≤2 times the upper limit of the normal range
 - c. total bilirubin ≤ 1.5 times the upper limit of the normal range

- d. renal function: serum creatinine ≤1.25 times the upper limit of the normal range
- 7. Negative infectious disease screen (hepatitis B, C or HIV); and drugs of abuse (negative urine screen).
- 8. A female patient of childbearing potential (not surgically sterilized and less than one year postmenopausal) must have a negative pregnancy test (urine human chorionic gonadotropin) at entry (prior to injection), and must have used medically accepted contraception for at least one month prior to treatment. Note: Women of childbearing potential and men must be advised to use a medically accepted method of contraception for at least 12 months following treatment.
- 9. Willing to provide a blood sample for HLA typing, if not done previously with available results

4.2 Exclusion Criteria

Patients will be excluded from this study if they meet any of the following criteria:

- 1. Eye disease other than RP that impairs visual function (including retinal vascular disease, elevated intraocular pressure/glaucoma, severe posterior uveitis, clinically significant macular edema), or media opacity precluding visual exam, as well as patients who require other intravitreal therapies
- 2. Pseudo-RP, cancer-associated retinopathies (CAR, MAR) excluded as part of differential diagnosis
- 3. History of malignancy, end-stage major organ disease (heart failure, significant arrhythmias, stroke or transient ischemic attacks, diabetes, immunosuppressive or autoimmune state, major psychiatric disorder, epilepsy, thyroid disease, COPD, renal failure, or any chronic systemic disease requiring continuous treatment with systemic steroids, anticoagulants or immunosuppressive agents.
- 4. Known allergy to penicillin or streptomycin.
- 5. Known allergy to or history of adverse reaction to fluorescein.
- 6. History of adverse reaction to DMSO.
- 7. Unable or unwilling to undergo genetic testing, pupil dilation, topical anesthesia or any protocol-required procedure.
- 8. Women who are nursing or who are planning to nurse during the 12 months that would follow study treatment.
- 9. Any circumstance that in the opinion of the investigator, would interfere with participation in, or compliance with the study protocol

- 10. Treatment with corticosteroids (systemic, periocular or intravitreal) or any other non-approved, experimental, investigational or neuroprotectant therapy (systemic, topical, intravitreal) in either eye within 90 days of study enrollment
- 11. Cataract surgery within three months prior to enrollment or anticipated to need cataract surgery within a year of treatment
- 12. Participation in a clinical trial for eye disease within 6 months.

4.3 Subject Withdrawal Criteria

Subjects may withdraw from the study at any time. Subjects may be discontinued from the study for any of the following reasons:

- Withdrawal of consent by the subject
- Development of intolerable AEs during the study
- Major protocol violation
- Lost to follow-up
- Any event that prevents the subject from meeting the study requirements

The investigator may also withdraw a subject at any time at his/her discretion. The sponsor reserves the right to terminate the study or withdraw any subject from the study for any reason at any time.

In addition, the sponsor reserves the right to temporarily suspend or prematurely discontinue this study either at a single site or at all sites at any time and for any reason. If such action is taken, the sponsor will discuss this with the investigator (including the reasons for taking such action) at that time. The sponsor will promptly inform all other investigators and/or institutions conducting the study if the study is suspended or terminated for safety reasons, and will also inform the regulatory authorities of the suspension or termination of the study and the reason(s) for the action. If required by applicable regulations, the investigator must inform the IRB promptly and provide the reason for suspension or termination.

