The investigational product (jCell) is a live suspension of $0.5-3.0 \times 10^6$ human retinal progenitor cells (hRPC) suspended in clinical grade medium. The hRPC are of allogeneic human fetal origin. Study subjects will receive a single dose of either 0.5, 1.0, 2.0, 3.0 x 10^6 jCell as an intravitreal injection under topical anesthesia into the eye with the worst visual acuity.

Duration of treatment:

Treatment with jCell consists of a single intravitreal injection. The injection procedure itself takes approximately 2 minutes. Patients will be released to home on the day of injection. Study subjects will be followed for one year post-injection under this protocol with a separate protocol planned for two additional years of long term follow up.

Criteria for Evaluation:

Efficacy:

Efficacy will be assessed based on a series of ophthmalogic assessments at specified timepoints, including best corrected visual acuity (BCVA), spectral domain optical coherence tomography (OCT), electroretinogram (ECG), visual field testing (where appropriate), fluorescein angiography, autofluorescence and a visual quality of life

NAME OF COMPANY: jCyte, Inc	SUMMARY TABLE	(For national Authority Use Only)
NAME OF FINISHED PRODUCT: iCell	Volume:	
NAME OF ACTIVE INGREDIENT:	Page:	
human retinal progenitor cells	Reference:	

questionaire (VFQ-25). In addition, several low vision assessment tools may be explored in subsets of subjects in order to better understand which assessments may be most useful for this type of treatment approach. None of these assessments are invasive.

Safety:

Safety will be assessed on an ongoing basis by adverse events, identification of dose-limiting toxicities (if any), physical examinations and vital signs, clinical laboratory values, and anti-drug antibodies. In addition, specific ophthalmalogic tests to monitor safety will be performed, including slit lamp and fundus examiniation, B-scans and intraocular pressure (IOP). Additional ophthalmalogic tests described above will also contribute to safety monitoring.

Clinical safety data will be reviewed on an ongoing basis. Safety data will undergo formal review by a DSMB following completion of each dose level 1 in Cohort 1 before initiation of the next dose level in Cohort 1, and before the initiation of the same dose level in Cohorty 2.

Statistical methods:

Background and demograhic data will be summarized for all subjects using descriptive statistics.

Efficacy:

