3.0 STUDY DESIGN

This is a prospective, multicenter, open-label, single-arm, Phase I/II trial of hRPC (jCell) for the treatment of retinitis pigmentosa (RP). Study subjects will be screened for eligibility, informed consent obtained, baseline studies of primary and exploratory endpoints performed. Then the subjects will be enrolled into one of two cohorts. Cohorts will be treated consecutively for each dose level, with review of safety data at scheduled intervals. That is, once a dose level is completed in Cohort 1, the enrollment of Cohort 2 subjects into that dose level can be initiated assuming no safety issues in Cohort 1 subjects at that dose level. Subjects will be entered into a treatment cohort based upon the order of enrollment at each of the study sites. Subjects in both cohorts will be followed for one year under this protocol and will be encouraged to participate in a follow-on study of long term safety and tolerability for an additional two years at study completion.

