3.3 Study Duration

The overall duration of the study is anticipated to be approximately 2 years. The study will be considered to have started when the first site is initiated. The study will be considered to have finished after the last subject has completed the last follow-up visit in the study (12 months following treatment).

All subjects who receive jCell treatment will be closely monitored throughout the observation period. All subjects who receive treatment with jCell will be encouraged to participate in a follow-on study to assess potential long term effects (safety and efficacy) of jCell treatment. The follow-on study is planned to include an at least two years of additional subject monitoring; additional follow up visits will be scheduled at least every 6 months with

monitoring to include medical history and physical exam, vital signs, safety lab tests (as at other visits), urinalysis, adverse events, BCVA and slit lamp/fundus exam at each visit; and additional ophthalmic exams at specified visits. More frequent visits will be scheduled during the initial or follow-on study as appropriate should this be indicated by safety concerns.

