4.4 Discontinuation/Withdrawal Procedures

If a subject is withdrawn from the study (i.e., ceases participation in the study prior to completion of the assessments planned in the protocol), the primary reason should be recorded in the case report form (CRF). Investigators should make every effort to capture withdrawal assessments, which will be recorded in the CRF.

The investigator will provide or arrange for appropriate follow-up (if required) for subjects withdrawing from the study, and will document the course of the subject's condition.

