8.0 ASSESSMENTS

8.1 Safety Assessments

8.1.1 Adverse Events

Subjects will be monitored for AEs from the time the subject receives a study number until the study end or early termination. Adverse events that occur between clinic visits will be elicited by direct, non-leading questioning or will be recorded if offered voluntarily by the subject. Further details for AE reporting can be found in Section 9.

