9.2 Serious and Unexpected Adverse Events

A serious adverse event is one which:

- is fatal or life threatening,
- is permanently or significantly disabling, or

• requires in-patient hospitalization or prolongation of hospitalization

An unexpected adverse experience is one which:

- is not previously reported with the agents or procedures being undertaken, or
- is symptomatically and pathophysiologically related to a reported toxicity but differs because of greater severity or increased frequency.

Important medical events that may not result in death, be life-threatening, or require hospitalization may be considered an SAE when, based upon appropriate medical judgment, they may jeopardize the subject and may require medical or surgical intervention to prevent one of the outcomes listed in the above definition.

The Investigator must report all SAEs and all deaths to the study sponsor or designee immediately by telephone and in writing within five (5) days. A toll free number and an SAE reporting form to report such events will be provided. See also section 11 with respect to administrative responsibilities.

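### Protocol 4.3 lets an injected subject be discontinued for an intolerable AE or major violation; this stops no treatment but ends the scheduled eye exams, and the SAP pools the exit exam with Month 12

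*Protocol*

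**What the plan says.** The synopsis, under duration of treatment, states: "Treatment with jCell consists of a single intravitreal injection". Protocol 4.3 lists reasons for which a subject may be discontinued from the study. They include "Development of intolerable AEs during the study" and a major protocol violation. The same section also lets the investigator withdraw a subject at his or her discretion, and the sponsor for any reason.

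Section 4.4 describes a withdrawn subject as one who "ceases participation in the study prior to completion of the assessments planned in the protocol". It asks for best efforts at withdrawal assessments and adds: "The investigator will provide or arrange for appropriate follow-up (if required) for subjects withdrawing from the study, and will document the course" of the condition.

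On AEs, 8.1.1 sets a window: "Subjects will be monitored for AEs from the time the subject receives a study number until the study end or early termination". Section 9.1 requires every AE after consent to be recorded on the CRF, and 11.1 requires all AEs to be recorded and reported to the sponsor. Neither gives an end date. Section 9.2 also gives none: "The Investigator must report all SAEs and all deaths to the study sponsor or designee immediately by telephone".

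Section 3.3 promises close monitoring of treated subjects during the observation period and more frequent visits where safety concerns call for them. It also says: "All subjects who receive treatment with jCell will be encouraged to participate in a follow-on study to assess potential long term effects". Section 3.0 words the same invitation differently: subjects "will be encouraged to participate in a follow-on study of long term safety and tolerability for an additional two years at study completion".

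Protocol 7.6 makes Month 12 and Early Termination one visit. The SAP keeps them as one time point for BCVA (9.1), laboratory data (10.3) and the Appendix C shells for IOP, B-scan, OCT, ERG and others. SAP 8.3 uses observed data only, and no rule assigns an exit exam to its actual time.

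**The concern.** In a repeat-dose trial, discontinuing for toxicity removes exposure. Here the cells are already in the eye, so discontinuing an injected subject removes only observation. Safety and tolerability are the primary objective. Several criteria in 3.2.2 (persistent IOP rise, retinal detachment, epiretinal membrane, tumor formation) may appear or evolve late and need scheduled exams to detect. An exit for an intolerable AE depends on the safety outcome, so the missing exams would fall on eyes already known to have had trouble.

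The second issue is presentation. An exit exam done weeks or months after injection is averaged or counted with one-year results, and a reader must go to the listings to separate them.

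**Working it through.** **Planned numbers.** Each vision cohort has dose cells of 4, 4, 3 and 3, so 2 × (4 + 4 + 3 + 3) = 28, matching the stated maximum. SAP section 4 gives no formal basis for this size. Neither document gives a dropout rate, so everything below is per exiting subject.

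**Inputs.** Visit days come from protocol Table 2 and 7.5: Day 28, Month 2 (Day 60), Month 3 (Day 90), Month 4 (Day 120), Month 5 (Day 150), Month 6 (Day 180) and Month 9 (Day 270). B-scans after Day 7 are at Months 3, 6 and 12. Month 12 is assumed to be Day 365, with Day 360 in brackets. The exit exam is assumed done, so it takes the place of the Month 12 visit.

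**Follow-up lost.** Days lost = 365 − exit day [360 − exit day]. Share of planned subject-days = days lost ÷ (365 × n), with 365 × 4 = 1,460 and 365 × 3 = 1,095.

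| Exit after | Visits lost before Month 12 | B-scans lost | Days lost | Share, n = 4 | Share, n = 3 |
|---|---|---|---|---|---|
| Day 28 | 6 (M2, M3, M4, M5, M6, M9) | 2 (M3, M6) | 337 [332] | 23.1% | 30.8% |
| Month 3 | 4 (M4, M5, M6, M9) | 1 (M6) | 275 [270] | 18.8% | 25.1% |
| Month 6 | 1 (M9) | 0 | 185 [180] | 12.7% | 16.9% |

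These are days of scheduled follow-up. They are also days of lost AE collection only if 8.1.1 governs over 9.1, 9.2 and 11.1.

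**Weight of one subject.** In a cohort-by-dose cell, 1/4 = 25% or 1/3 = 33%. With cohorts combined by dose, 1/8 = 12.5% or 1/6 = 16.7%. Over the whole trial, 1/28 = 3.6%.

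**Effect on the combined row.** The exit exam is 337, 275 or 185 days earlier than the Month 12 exams beside it. As an illustration with assumed values, let completers gain 5 letters and let the one early exit be at −10 or −30 letters. The row mean is [5(n − 1) + L]/n:

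- n = 3: (10 − 10)/3 = 0.0, or (10 − 30)/3 = −6.7
- n = 4: (15 − 10)/4 = +1.25, or (15 − 30)/4 = −3.75

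Completers alone give +5.0. An exit exam better than the completers' results would move the mean the other way. In either case the row mean describes no single time after injection.

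**The case against.** The strongest case on the other side is that the clause is permissive and surrounded by safeguards. Section 4.3 says may, one-year follow-up is the default, and 3.3 answers a safety concern with more visits. Section 4.4 asks for follow-up and documentation. The triggering AE stays in the TEAE and SAE tables, with duration and outcome required by 9.1. The follow-on study includes BCVA and slit lamp/fundus exams at least every six months, and 7.6 places consent for it at the Month 12 or Early Termination visit. The SAP row is openly labelled, Table 14.1.1 shows discontinuations by reason and cell, and the listings give assessment dates and study days. No hypothesis is tested. With cells of three or four, any single loss looks large.

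Most of this stands, and it rules out stronger readings. A reader might infer that the protocol requires harmed subjects to be removed, that all AE recording stops at exit, or that their events vanish from the safety tables. The documents support none of these. Nor is 4.3 only about injected subjects: study numbers are given at consent, so it also covers exits before injection.

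The safeguards still leave a gap. Follow-up under 4.4 is only if required, with no exams, timing or CRF named. The follow-on study is voluntary and under a separate protocol, and 3.0 ties it to study completion. The provisions in 3.3 do not say that they apply to a subject already discontinued. Traceable listings do not unmix the summary row.

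**Conclusion.** The point holds as a modest, inexpensive improvement. No sentence keeps an injected subject on the scheduled exams to Month 12 when the reason for exit is an AE or a deviation. The AE sections disagree about whether collection continues after exit, and the SAP mixes exit and Month 12 results. The effect is conditional: with no such exits, nothing is lost. With one, 25% to 33% of a cohort-by-dose cell is missing at the later scheduled visits, and the same share of its Month 12/Early Term row comes from an earlier time. These figures assume one exit per cell, illustrative exit times and a completed exit exam. Nothing in the documents shows how likely such an exit is.

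**What to change.** In 4.3, with matching text in 4.4 and 8.1.1, state that for an injected subject an AE or protocol deviation alone does not end scheduled visits or AE collection. The rule should apply whether the exit would be made under the listed reasons or under investigator or sponsor discretion; otherwise the discretion clauses offer a way round it. The subject is followed to Month 12 unless consent is withdrawn, the subject is lost or dies, or the study is terminated. Individual assessments judged unsafe may be omitted.

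In the SAP, show Early Termination results in a row separate from Month 12, so that both remain visible.

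The cost is a short amendment needing IRB approval under 11.2, a few visits already in the schedule, and slightly more table work. SAP Appendices A and B already allow tables to be reorganized during programming. If every subject has already passed Month 12, only the SAP change affects this trial.

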4.4 Discontinuation/Withdrawal Procedures

If a subject is withdrawn from the study (i.e., ceases participation in the study prior to completion of the assessments planned in the protocol), the primary reason should be recorded in the case report form (CRF). Investigators should make every effort to capture withdrawal assessments, which will be recorded in the CRF.

The investigator will provide or arrange for appropriate follow-up (if required) for subjects withdrawing from the study, and will document the course of the subject's condition.

5.0 SUBJECT REGISTRATION

At the time informed consent is obtained, qualified subjects will be assigned a study number. At the time a study number is assigned by the Sponsor or designee, the interval between the CONFIDENTIAL 20 of 41 last subject treated and the planned treatment of the new subject will be assessed to assure that it meets study requirements for separation of patient treatments.

6.0 TREATMENT PLAN

6.1 Dose and Schedule

All subjects will receive a single intravitreal injection of hRPC at the assigned dose into the eye with the poorest visual acuity or, if vision is comparable in both eyes, the non-dominant eye. After topical anesthesia, a single 50 microliter suspension of cells (0.5, 1, 2 or 3 million) will be delivered under direct visualization into the vitreous cavity using a 30 g needle. This treatment does not require surgical detachment or manipulation of the retina. The injection procedure itself takes approximately 2 minutes. Following 60 minutes of observation with no serious clinical symptoms or manifestations (IOP < 30 mm Hg and vital signs comparable to pre-treatment), subjects will be released to home on the day of injection. Please refer to the study procedure manual for details of patient preparation and monitoring.

The schedule of observations and assessments during the study are summarized in Table 2.

jCyte, Inc Protocol No. JC-01

				I able A	2 Sche	aule of .	Assessm	ents (JC	Ĵ - 01)							
Timepoint	Scr	BL*	Day 0	Day 1	Day 2	Day 7 ⁷	Day 14 ⁷	Day 21 ⁷	Day 28 ⁷	M 2 ⁸	M3 ⁸	M4 ⁸	M5 ⁸	M6 ⁸	M9 ⁸	M12 or Early Term
Written informed consent	Х															
Medical history (MH)	Х	x*														Х
Physical examination (PE)	Х	x*														х
Brief MH and PE				х		Х			X		X			Х		
HLA typing	Х															
Weight	Х	x*	Х			Х										Х
Vital signs	Х	х	Х	Х	Х	х	Х	х	Х	Х	Х	Х	Х	Х	х	Х
Pregnancy test	Х	x*														х
Safety laboratory tests ¹	Х	x*				х			Х		Х			Х		Х
Infectious disease tests ²	Х	x*														
Urinalysis ³	Х	x*									Х			Х		х
Electrocardiogram	Х	x*	х	Х												
Slit lamp and fundus exam	Х	x ⁴		х	х	Х	Х	х	X	х	X	X	Х	Х	х	Х
BCVA (ETDRS)	Х	x	х	х	х	Х	Х	х	X	х	X	X	Х	Х	х	Х
ERG	x ⁹	x ⁹												Х		Х
IOP		x	х	х	х	Х	Х	х	X	х	X	X	Х	Х	х	Х
OCT		х							Х		Х			Х	х	Х
FA		х												x ⁶		х
AF		х												Х		х
VF (if applicable)		x												Х		Х
B-scan		х				Х					X			Х		Х
Exploratory non-invasive visual assessments (optional)		х									х			х	х	х
Study Drug Injection			х													
Con Meds			Х	х	х	х	х	х	х	х	х	х	Х	Х	Х	Х
Adverse events			х	х	х	х	х	х	х	х	х	х	Х	Х	Х	Х
Blood sample for Ab testing ⁵		х					Х		х							Х
Written consent for FU study																Х
		·				*	*	·					•			

 Table 2 Schedule of Assessments (JC -01)

Hematology (minimally Hct, Hgb, CBC with diff, plt), coagulation panel and blood chemistries (minimally AP, ALT, AST, BUN, Cr, total bilirubin, serum electrolytes, glucose, calcium, phosphate, albumin and total protein) ²Hepatitis B and C, HIV ³ Drug screen included at screening visit ⁴ Fundus photographs at baseline ⁵ Testing for Panel Reactive Antibodies (PRA) and Donor Reactive Antibodies (DRA) ⁶ Only if cystoid macular edema (CME) is observed on OCT ⁷ Visit window +/- 1 day ⁸ Visit window +/- 4 days ⁹ERG can be performed at screening to confirm eligibility; if so, does not need to be repeated at baseline. *Day -30 to 0. Does not need to be repeated if Day 0 is within 30 days of screening.

CONFIDENTIAL

22 of 41

